### Patients prematurely discontinuing study drug:

Patients who discontinue study drug prematurely should ideally be observed until study end as if they were still receiving blinded study treatment. There are 4 Options for observing patients after premature drug discontinuation. See [Section 3.3.4.1](#)

**Early D/C Option 1:** For patients who prematurely discontinue taking study drug who are willing to conduct the remaining visits, the following should be performed:

- EOT Visit must be performed within 7 days of last intake of study drug, or as soon as possible.
- Thereafter, patients should be followed up according to the regular visit schedule through Visit 16.
- A Follow-Up Visit is not necessary if the patient discontinued >4 weeks prior to Visit 16. If a patient discontinues <4 weeks prior to Visit 16, a Follow-up Visit will be performed 28 days after the EOT Visit.

**Early D/C Option 2:** For patients who prematurely discontinue taking study drug who are willing to conduct the remaining visits over the phone, the following should be performed:

- EOT Visit must be performed within 7 days of last intake of study drug, or as soon as possible.
- A Follow-up Visit will be performed 28 days after the EOT Visit.
- Thereafter, patients should be followed up over the phone according to the regular visit schedule through Visit 16. See [Section 3.3.4.1](#) for Early D/C Option 2 which details the assessments to be conducted via phone.

**Early D/C Options 3 and 4:** For patients who prematurely discontinue study drug and agree to be contacted or have information collected from an alternative source at the end of the study, the following should be performed:

- EOT Visit must be performed within 7 days of last intake of study drug, or as soon as possible.
- A Follow-up visit will be performed 28 days after the EOT Visit.
- Occurrence of psychiatric illness/relapse and vital status must be collected approximately 28 weeks after the patient was randomised.

#### 6.2.2.1 Withdrawal/Taper Period

Patients who complete the 28 week treatment period will enter the withdrawal/taper period. When patients are randomised at Visit 2, they are also randomised to either abrupt withdrawal or slow taper of study drug. Vital signs, suicidality and adverse events will be closely monitored during this period.

Refer to [Section 7.3.4](#) for the withdrawal/taper analysis strategy.

### **6.2.3 Follow up period and trial completion**

Patients who complete the treatment and withdrawal/taper periods will have a Follow-Up Visit performed at Week 32. Patients who enter the withdrawal/taper period, but discontinue taking their study drug will have a Follow-up Visit as planned at Week 32.

For patients who prematurely discontinue taking study drug who are willing to conduct the remaining in-clinic and phone visits (Early D/C Option 1), a Follow-Up Visit is not necessary if the patient discontinued >4 weeks prior to Visit 16. If a patient discontinues <4 weeks prior to Visit 16, a Follow-up Visit should be performed 28 days after the EOT Visit.

A Follow-Up Visit will be performed 28 days after the EOT Visit for patients who prematurely discontinue taking study drug and agree to conduct the remaining visits over the phone or who agree to be contacted or have information collected from an alternative source at the end of the study (Early D/C Options 2-4).

Occurrence of AEs since last visit will be documented and will be managed in accordance with [Section 5.2.6](#). All AEs and/or SAEs persisting after trial completion must be followed up until they have resolved, have been sufficiently characterized, or no further information can be obtained.

## 7. STATISTICAL METHODS AND DETERMINATION OF SAMPLE SIZE

### 7.1 STATISTICAL DESIGN - MODEL

This is a randomised, double-blind, parallel group, multi-centre trial aiming to show superiority of BI 409306 to placebo as an intervention to prevent relapse in patients with schizophrenia. All patients will be treated for 28 weeks.

The primary objective of the statistical analysis is to determine whether BI 409306 significantly reduces the risk of relapse in comparison to placebo.

The estimand of primary efficacy interest is the test of the hazard ratio of BI 409306 (25 mg q.d. and 50 mg q.d. pooled) vs. placebo using the Wald test for the treatment effect in a stratified Cox proportional hazards model stratified by country, on the full analysis set using the ITT follow-up analysis period. Refer to Sections [7.2](#) and [7.3](#) for more details.

### 7.2 NULL AND ALTERNATIVE HYPOTHESES

The trial will follow a hierarchical testing strategy. The first hypothesis for the superiority testing of the primary endpoint time to first relapse is (HR = hazard ratio):

$H_0: HR_{BI\ 409306 / placebo} = 1$  vs.  $H_a: HR_{BI\ 409306 / placebo} \neq 1$ , where  $HR_{BI\ 409306}$  is the hazard ratio for the pooled active treatment arms (i.e. BI 409306 50 mg q.d. and BI 409306 25 mg q.d.), over 28 weeks (excluding the withdrawal/taper period)

Superiority will be declared if the hazard ratio between BI 409306 vs. placebo is statistically significantly less than 1 at the two-sided type I error level  $\alpha = 0.05$ .

If the first hypothesis test is determined to be statistically significant, the individual doses will be tested for superiority using Hochberg's step-up test. The method will be to perform the statistical tests and rank the p-values for the individual doses vs. placebo. Let  $p_{(1)} \geq p_{(2)}$  be the two-sided p-values. The corresponding null hypotheses are  $H_{0(1)}$  and  $H_{0(2)}$ .

$H_{0(1)}: HR_{BI\ 409306 / placebo} = 1$  vs.  $H_{a(1)}: HR_{BI\ 409306 / placebo} \neq 1$ , where  $HR_{BI\ 409306}$  is the hazard ratio for the BI 409306 dose with the highest p-value

$H_{0(2)}: HR_{BI\ 409306 / placebo} = 1$  vs.  $H_{a(2)}: HR_{BI\ 409306 / placebo} \neq 1$ , where  $HR_{BI\ 409306}$  is the hazard ratio for the BI 409306 dose with the lowest p-value

Step 1: If  $p_{(1)} \leq 0.05$  then both hypotheses are rejected and both doses are declared statistically significant and testing ends. If  $p_{(1)} > 0.05$ , then  $H_{0(1)}$  is not rejected and the testing proceeds to Step 2.

Step 2: If  $p_{(2)} \leq 0.025$ , then  $H_{0(2)}$  is rejected and this dose is declared statistically significant. If  $p_{(2)} > 0.025$ , then all doses fail.

The remaining alpha after the testing of the primary endpoint (Steps 1 and 2) will be used to test the key secondary endpoint of change from baseline in PANSS positive symptoms. The hypotheses to be tested are:

- H0(3): Mean change from baseline of PANSS positive symptom score after 28 weeks of treatment with BI 409306  
≥ Mean change from baseline of PANSS positive symptom score after 28 weeks of treatment with placebo
- Ha(3): Mean change from baseline of PANSS positive symptom score after 28 weeks of treatment with BI 409306  
< Mean change from baseline of PANSS positive symptom score after 28 weeks of treatment with placebo

The first of the key secondary hypothesis to be tested will be based on the pooled active treatment arms (i.e. BI 409306 50 mg q.d. and BI 409306 25 mg q.d.), over 28 weeks (excluding the withdrawal/taper period).

Similar to the primary endpoint, if the first hypothesis test (on the pooled doses) is determined to be statistically significant, the individual doses will be tested for superiority using Hochberg's step-up test as described above.

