### 7.7 DETERMINATION OF SAMPLE SIZE

Sample size considerations are given in Table 7.7: 1 based on background placebo relapse rates of 25% and 30% and for hazard reductions for the combined BI 409306 groups vs.

placebo ranging from 45% to 55%, 80% power, a two-sided alpha = 0.05, and 20% dropout after six months.

Table 7.7: 1 Trial sample sizes for selected assumptions of hazard ratios and proportions of placebo failures, with 20% dropout, 80% power, and  $\alpha=0.05$

Placebo failure rate	Hazard reduction a for BI 409306 (both groups combined) to placebo		
	55% a	50% a	45% a
30%	305	385	494
25%	372	470	603

a 55% hazard reduction is the same as a hazard ratio of 0.45; 45% hazard reduction is the same as a hazard ratio of 0.55

The sample size selected was 385 under the assumption that the relapse rate for placebo is 30% and the hazard reduction for BI 409306 is 50%. One hundred twenty-nine (129) patients will be randomised per treatment group in a 1:1:1, making the target total number of randomised patients to be 387.

Seventy-four (74) events (relapses) are needed to be observed to meet the trial objective of 80% power for the comparison of BI 409306 (N=258 for 25 mg q.d. and 50 mg q.d. combined) to placebo (N=129). This will not be an event driven trial, so the trial will end when all randomised patients have reached 6 months exposure, regardless of number of conversions observed.

Calculations were performed using ADDPLAN® 6.1.1 statistical package by [REDACTED].

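### After a significant pooled-dose test, Hochberg's 0.025 step adds nothing to the 0.05 guarantee over the two dose claims and costs some power to name a dose

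*Protocol*

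**What the plan says.** Protocol 7.2, repeated in SAP 7.4, sets out a hierarchy for time to first relapse. The pooled active arms are compared with placebo at two-sided 0.05. Only if that is significant does the plan go on to single doses, where "the individual doses will be tested for superiority using Hochberg's step-up test". In Step 1, if the larger of the two p-values is at most 0.05, both doses are declared. In Step 2, if the larger exceeds 0.05, the other dose is declared only at p ≤ 0.025; failing that, no dose is declared.

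The key secondary endpoint (PANSS positive score) then receives whatever alpha remains after Steps 1 and 2, and no amount is stated. The same two-stage scheme applies there: "if the first hypothesis test (on the pooled doses) is determined to be statistically significant, the individual doses will be tested for superiority", again by Hochberg (Protocol 7.2; SAP 7.5.1).

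The sample size in Protocol 7.7 is set for the pooled comparison only: "Seventy-four (74) events (relapses) are needed to be observed to meet the trial objective of 80% power". No power target is given for a single dose. SAP section 4 records that recruitment was stopped early, that power is reduced in consequence, and that quick results are wanted for planned phase III trials. The final number of patients is not given.

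**The concern.** The pooled test and Hochberg both protect against the same event: a false dose claim when neither dose works. Once the first has been passed at 0.05, the second corrects for that multiplicity again. The price is paid in one configuration: the pooled test is significant, the better dose has p between 0.025 and 0.05, and the other dose has p above 0.05. The trial is then positive overall but formally names no effective dose. That is an awkward result for a two-dose phase II trial meant to prepare phase III, and a smaller trial makes it more likely.

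**Working it through.** **Inputs.** Protocol 7.7 gives "80% power, a two-sided alpha = 0.05, and 20% dropout after six months"; "the relapse rate for placebo is 30% and the hazard reduction for BI 409306 is 50" per cent; and "One hundred twenty-nine (129) patients will be randomised per treatment group in a 1:1:1" allocation. Protocol 7.1 gives 28 weeks of treatment. My assumptions are exponential relapse times, dropout as independent exponential censoring over the 28 weeks, and no country strata.

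**1. The plan's own figures.** Schoenfeld's formula with a placebo share of 1/3:

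D = (1.960 + 0.842)² / [(1/3)(2/3)(ln 0.5)²] = 7.849 / 0.1068 = 73.5, rounded up to 74. This agrees with the protocol.

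Per 28 weeks, the placebo relapse hazard is −ln 0.70 = 0.357 and the dropout hazard is −ln 0.80 = 0.223. The probability of an observed relapse is λ/(λ+γ) × [1 − exp(−(λ+γ))]: 0.271 on placebo and 0.147 on active treatment at hazard ratio 0.5. The average is (0.271 + 2 × 0.147)/3 = 0.188, so N = 73.5/0.188 = 391, against 385 in the protocol (1.5% apart). The other five cells of Table 7.7:1 agree within 1.6%. At 129 per arm this gives about 34.9 placebo relapses and 18.9 per active arm, about 73 in all.

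**2. Single tests, normal approximation.**
- Pooled: SE = √(1/34.9 + 1/37.9) = 0.235; 0.693/0.235 = 2.95; power Φ(2.95 − 1.96) ≈ 84%.
- One dose: SE = √(1/34.9 + 1/18.9) = 0.285; 0.693/0.285 = 2.43; power Φ(2.43 − 1.96) ≈ 68% at 0.05 and Φ(2.43 − 2.24) ≈ 57% at 0.025.

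**3. Error control without Step 2.** Suppose each dose is tested at two-sided 0.05 after the pooled test passes.
- Both dose nulls true: all three hazards are equal, so the pooled null is true. A dose claim needs the pooled test to reject, so its probability is at most 0.05.
- One dose null true: only that dose can be falsely declared, with probability at most 0.05.
- Doses acting in opposite directions so that the pooled hazard ratio is 1: both dose nulls are false, and the only possible false rejection is the pooled one, at most 0.05.

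This is closed testing with the pooled test serving as the intersection test. Simulation agrees. With both doses null, the chance of any false rejection (pooled test included) is 4.9% under either rule. With one dose null and the other overwhelmingly effective, it is 5.0% under either rule.

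**4. Power.** Every Hochberg rejection is also a rejection at 0.05, so the closed test never loses a claim. Chance of declaring at least one dose:

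| Hazard ratios (25/50 mg) | Per arm | Hochberg | Each dose at 0.05 |
|---|---|---|---|
| 0.5 / 0.5 | 129 | 74.8% | 80.5% |
| 0.7 / 0.7 | 129 | 27.9% | 33.9% |
| 0.7 / 0.5* | 129 | 53% | 58% |
| 0.75 / 0.5 | 129 | 50.5% | 54.3% |
| 0.8 / 0.5* | 129 | 44% | 47% |
| 1 / 0.5 | 129 | 27.9% | 28.5% |
| 0.5 / 0.5 | 100 | 62.4% | 69.5% |
| 0.5 / 0.5 | 80 | 51.6% | 59.6% |
| 0.5 / 0.5 | 60 | 38.9% | 47.2% |

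Rows marked * use the normal approximation to the log hazard ratio; the others simulate the Wald test on exponential data (400,000 trials per row).

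In the design case the pooled power is 83.3%. Each dose is declared in 65.2% of trials under Hochberg and 68.0% at 0.05; both doses are declared in 55.5% under either rule. The pooled test is positive with no dose named in 83.3 − 74.8 = 8.5% of trials under Hochberg and 83.3 − 80.5 = 2.8% at 0.05. As a share of trials with a positive pooled test, that is 10.2% against 3.4%.

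**5. The key secondary endpoint.** Suppose 0.025 were passed on after a single-dose win. Take one dose null, the other overwhelmingly effective, and the secondary endpoint null and independent. The null dose is falsely declared with probability 0.05; otherwise the secondary is tested at 0.025. The total is 0.05 + 0.95 × 0.025 = 0.074, with or without Hochberg. If alpha passes only when both doses are declared, a secondary test with a null dose still in play requires a dose error to have occurred already, and the total stays at 0.05.

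**The case against.** The planned procedure is valid and coherent, and a reader might wrongly infer from this point that it inflates the error rate. It does not; it is conservative. Nor is it true that Step 2 lowers no error rate at all. When neither dose works, it reduces the actual chance of declaring any dose from 4.3% to 3.1% counting both directions (about 2% to 1.5% counting benefit only). It leaves the guaranteed maximum of 0.05 unchanged, and that is the only protection the plan claims.

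The powered objective is the pooled comparison, and a cautious follow-on step is a defensible choice in phase II. The gain is also smallest where naming the right dose matters most. With equal effects, the extra declarations pick either of two equally good doses; if only one dose works, the pooled test is the bottleneck and the gain is under 1 point. Protocol 4.1.2 expects target exposure in 49% of subjects at 25 mg and about 94% at 50 mg, so equal effects are not the obvious case. All of this limits the size of the point, but none of it gives a reason to keep Step 2.

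A reader might also infer that Hochberg would leave phase III without a dose. The documents do not support that. SAP 7.4.1 produces hazard ratios with confidence limits for treatments against placebo, Protocol 7.3.5 plans exposure–response modelling if the primary analysis shows an effect, and nothing ties dose selection to the Hochberg label. Even with the change, about 3% of design-case trials would be positive on the pooled test with no dose named.

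**Conclusion.** The point stands as an improvement in efficiency at no cost in guaranteed error control. It is not an error-rate violation. The 0.025 threshold bites only when the other dose has p above 0.05. Removing it raises the chance of naming at least one dose by about 6 points in the design case, about 3 to 5 points at hazard ratios of 0.7–0.8 for 25 mg and 0.5 for 50 mg, and under 1 point if only one dose works. At 60 to 100 per arm with hazard ratio 0.5 for both doses, the gain is about 7 to 8 points; those arm sizes are assumed, because the documents do not give the final number.

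The error argument depends on there being exactly two doses behind one pooled test, and it covers the primary-endpoint claims. Control over the family that includes the key secondary endpoint depends on the alpha-passing rule, which the plan leaves undefined under either procedure.

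**What to change.** Before unblinding, replace Steps 1 and 2 in Protocol 7.2 and SAP 7.4 with:

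> If the pooled test is significant at two-sided 0.05 with HR < 1, each dose is tested against placebo at two-sided 0.05 (closed testing). A dose is declared effective if p ≤ 0.05 and HR < 1.

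In the same edit, replace the sentence that hands on the alpha remaining after Steps 1 and 2 (Protocol 7.2; SAP 7.5.1), which would otherwise refer to deleted text:

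> The key secondary endpoint is tested at two-sided 0.05 only if both doses are declared on the primary endpoint; otherwise it is descriptive.

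On the key secondary endpoint, use the same pooled-then-each-dose closed test at the level passed to it, and align the reference to remaining alpha in Protocol 7.3.2 and SAP 7.5.1.

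The change needs no new data, no more patients and no change to the Cox model. It does loosen a prespecified decision rule: the previous change to Protocol 7.2 was made by a global amendment requiring ethics and authority approval, and the SAP is already at version 4. It also rules out formal secondary testing after a single-dose win, which the present undefined wording leaves open. If the treatment code has already been broken, keep the planned rule for formal claims.

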### 7.3 PLANNED ANALYSES

Two patient populations are defined:

- The treated set (TS) includes all patients who were dispensed study medication and were documented to have taken at least one dose of investigational treatment
- The full analysis set (FAS) includes all patients in the treated set with at least one post-baseline measurement of any type

No per protocol population will be used for analyses; however protocol violations will be identified and listed.

Analysis sets will be fully defined in TSAP.

Three analysis periods are defined:

- **Intent to Treat (ITT) follow-up:** from treatment start date until the end of the intended complete treatment period:

For patients who complete the trial according to the [flow chart](#), the withdrawal/taper period is not included. Additionally, if a patient happens to take drug for 29 weeks (i.e. 1 week longer than the planned 28 weeks) and then begin the withdrawal/taper period, the withdrawal/taper period will not be included.

For patients who discontinue prior to the 28 week treatment period, e.g. at week 25, the follow-up period until the end of week 28, is included.

- **Full follow-up:** from randomisation until the end of the trial, including all observed time on and off trial medication until the follow-up visit or the last date of contact:

For patients who discontinue trial medication according to the [flow chart](#), the withdrawal/taper period is included. Additionally, if a patient happens to take drug for 29 weeks (i.e. 1 week longer than the planned 28 weeks) and then begin the withdrawal/taper period, the withdrawal/taper period is included.

For patients who discontinue prior to the 28 week treatment period, e.g. at week 25, the follow-up period until the last contact date is included.

The full follow-up analysis period will be used as a sensitivity analysis to the ITT follow-up analysis.

- **On-treatment:** from treatment start date until the date of discontinuation of trial medication + 7 days:

For all patients this analysis period includes only the time on trial medication + 7 days after taken off trial medication.

For patients randomised to the withdrawal period, this will include 28 weeks of treatment, or for early discontinued patients, the time period on active treatment prior to discontinuation + 7 days, which corresponds to the 7 days abrupt withdrawal period.

For patients randomised to the taper period, this will include 28 weeks of treatment + the tapering period (of 7 days) + 7 days, or for early discontinued patients, simply the time period on randomised active treatment prior to discontinuation + 7 days (because tapering will not be done for patients discontinued early).

The on-treatment analysis period will be used to analyse safety.

### 7.3.1 Primary endpoint analyses

The primary endpoint is the time to first relapse as defined in [Section 2.1.2](#) over the ITT follow-up period (see definition in [Section 7.3](#)).

The treatment comparison strategy is specified in [Section 7.2](#). The treatment arms will be pooled according to dose, i.e. no distinction will be made between treatment arm randomised to taper or treatment arm randomised to withdrawal.

The equality of the hazard rates will be tested by the Wald test for the treatment effect in a stratified Cox proportional hazards model at the two-sided 5% significance level. The model includes the treatment effect as the only covariate and is stratified by country. Breslow's method for handling ties will be used.

The same stratified Cox proportional hazards model will be used to estimate the hazard ratio of BI 409306 vs. placebo and the asymptotic 95% Wald confidence interval. A hazard ratio of less than one favors BI 409306. The analysis will be implemented using SAS® PROC PHREG. Cox proportional hazard model assumptions will be verified.

In early discontinued patients, if the occurrence of a relapse cannot be determined between the time of discontinuation and last contact, it is assumed that no relapse has occurred. Patients who discontinue study medication will be followed until the end of the trial for the primary endpoint. Patients who are lost-to-follow up will be censored for the primary endpoint at the date of last known patient contact.

A sensitivity analysis will be conducted on the primary endpoint, using the Full Follow-up period (see definition above).

